6.2 Eligibility criteria

The criteria outlined here are to enter the study, ie the screening phase.

6.2.1 Inclusion criteria

- Clinical diagnosis of a Foot Ulcer, present on area that is measurable with a grid sheet (this
 can include plantar, calcaneus, dorsal, hallux, apex, or ankle based ulcers). This includes DFU,
 peripheral arterial disease related wound, or other aetiology.
- Foot ulcer present for at least 2 weeks.
- Adult patients aged > 18 years
- Patients with recurrent wounds, including multiple wounds, are eligible. The largest of the wounds, that is measurable with a grid sheet, will be selected for the trial.
- Mental capacity to give consent

6.2.2 Exclusion criteria

- Under the age of 18 years
- Unable to fully understand the consent process and provide informed consent due to either language barriers or mental capacity
- Limited life expectancy, i.e. undergoing palliative care
- Active infection in foot ulcer that cannot be managed in podiatry service (ie requires specialist secondary care intervention)
- Any personal objection to being administered a product containing porcine material.
- Patients who are participating in another research study involving an investigational product.
- The patient has concurrent (medical) conditions that in the opinion of the investigator may compromise patient safety or study objectives, including alcohol or drug dependency.
- Foot ulcer in area of the foot, e.g. in between toes, which would make exact ulcer size measurement impossible.
- Patient pregnant, actively planning to become pregnant, or lactating
- Ankle brachial index < 0.6, measured within 3 months of baseline visit

6.3 Early withdrawal of subjects

Patients have the right to withdraw from the trial at any time and without giving any reason. If a patient withdraws from the trial, any and all information gathered prior to the withdrawal will be excluded in the analysis, no further data collection will occur. If a patient does not attend a planned follow-up appointment then two more attempts will be made to contact the patient regarding the study. If still no contact can be made then the patient is deemed lost to follow-up and any collected study data will be retained.

If a female patient finds out that she is pregnant during the course of participating in the study, they will be requested to inform the research team immediately. The participant will be withdrawn from the study if allocated to the Granulox arm. Since the study is not blinded, there is no requirement for an unblinding procedure.

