5.3 Consent

Those eligible will be approached and provided with an information pack and consent form, which will be signed to indicate that informed consent has been given. Patients will be given ample time to consider taking part, more than 24 hours if they wish. The direct healthcare professional will first approach a patient about the study, and after verbal consent by the patient the healthcare professional themselves or a member of the research team can go through the informed consent process.

Patients are also allowed to consent to taking part when first approached as long as the study has been discussed with the patient and they have been given time to read the patient information leaflet and opportunity to ask any questions that they may have. Participants will receive no incentives and consent will be regarded as a process and not a one-off event. Participants are free to withdraw from the study at any time without the need to give any reasons for withdrawal. Their standard of care will not be affected by either declining to participate in the study or withdrawing during participation. Data collected up to the date of withdrawal will be retained for analysis.

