5.6.2 Secondary outcome measures

This study also aims to record wound characteristics and patient-related outcomes measures, as well as safety endpoints.

- Size and characteristics of foot ulcer, determined with PUSH score (week -2, 0, 3, 6, 9, 12)
- Grading of foot ulcer, using Texas Univ grading score (week -2, 0, 3, 6, 9, 12).
- Wound closure status (week 0, 3, 6, 9, 12)
- Mobility score, as determined by LifeSpace questionnaire (week 0, 6, 12)

- Visual Analogue Pain score (week -2, 0, 3, 6, 9, 12)
- Quality of life score, determined with EQ5D-5L and Charing Cross Venous Ulcer Questionnaire (week 0, 6, 12)
- Wound status check [healed, not healed, recurrence] and any incidences of adverse events (week 18)
- Patient withdrawal rates due to change in management (e.g. need for surgery)
- Wound infection rates, any other adverse events
- Patient experience and satisfaction with the Granulox product and treatment regime

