6. SUBJECTS

6.1 Anticipated number of research subjects

There is pilot data to base a *priori* sample size calculation on, but this concerns a single retrospective study (Hunt and Elg, 2016). In their study, they observed 37% (control) and 89% (Granulox) wound size change versus baseline measurement at 12 weeks. This would mean that 14 patients (7 in each arm) would be sufficient to have the trial powered to 80%. For this present trial, a more conservative approach is taken, see Table 4. The earlier published average healing rate of 25% is used as the anticipated minimum healing rate (Margolis, 1999). Since some patients may require surgical intervention or may withdraw, a hypothetical 20% dropout rate is calculated into the sample size (actual attrition rate is a study objective). A theoretical 1:1 allocation to the control and Granulox intervention group respectively will be applied. However, because the PUSH score is not known beforehand this may not be achieved if more patients are recruited into one of the two PUSH cohorts. Diabetic foot ulcers (DFUs) and other foot ulcers will be randomised from separate randomisation lists.

The primary outcome, average percentage decrease in ulcer size between baseline and 12 week follow-up is used for sample size calculation. Power calculations for sample size, 80% power and 5% significance, based on two-sided Mann-Whitney U-test. A priori power calculations using GPower 3.1 software, result in the following sample size summarized in Table 4. This is based on the DFU study by Hunt and Elg. A further 20 patients with non-diabetic foot ulcers will be recruited to pilot what impact Granulox has on those types of wounds.

Table 4, Sample size calculation

	Median change in DFU ulcer size at 12 weeks (presume decrease for both arms, ie one-tailed approach)	Standard Deviation
Arm A (hypothetical)	52%	30%
Arm B (hypothetical)	25%	30%
	Power beta of 80%, Alpha p-value of Sample size required without any dro	

Sample size with 20% attrition rate included: 40

Total of 40 DFU patients:

- 20 Patients to receive treatment as usual (TaU)
- 20 Patient to receive TaU plus Granulox spray

Plus 20 non-DFU foot ulcers:

- 10 Patients to receive treatment as usual (TaU)
- 10 Patient to receive TaU plus Granulox spray

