The CONSORT guidelines require a statement on the number of patients assessed for eligibility (Schulz, Altman & Moher 2010). The number of patients screened but who did not meet the inclusion criteria or who declined to participate will be recorded, as will any patients who are lost to follow-up (Appendix 3).

The calculation does take into account a 10% patient attrition rate (withdrawal and loss to follow-up), since this involves a study with at least two visits. Patients will be recruited from the adult (age 18+) population routinely seen by the evaluating clinical staff members.

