6.1.1 Randomisation

Following written consent at -2 weeks, participants will be observed for two weeks to establish healing rate. At the end of two weeks, patients are only eligible for the intervention phase if their wound has healed <50% in the preceding two weeks. At this point, week 0, participants are allocated at random to the control or Granulox intervention group, using a randomised sequence from the freeware randomisation programme, see https://www.randomizer.org/. The randomisation is stratified for ulcer size, with PUSH score of 5 or less, and 6 or above as the cut-off. This size has been determined as the average size of a presenting foot ulcer previously (Zimny et al, 2002).

Sequential envelopes with each next randomisation allocation will be used to achieve concealment and these will be kept in the research department. The researcher will then inform the regular healthcare professional for the participant in question, and the participant themselves, which treatment they've been allocated to. The researcher will dispatch a Granulox canister to the clinic where the participant will be seen. At this stage the twice weekly treatment (though three applications per week would be allowed if dressing change is more than twice a week) will commence.

As the study involves administration of a spray it is not possible to achieve blinding for the participants nor the researchers – it is recognised that this increases the risk of bias.

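### Sections 5.3 and 6.3 give opposite rules for withdrawn patients' data; following 6.3 can bias the interim-week and Cox analyses and leaves those patients' adverse events out of the safety analysis

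*Protocol*

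**What the plan says.** Three rules in the protocol govern the data of patients who leave.

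- Section 5.3 (Consent), on patients who choose to withdraw: "Data collected up to the date of withdrawal will be retained for analysis".
- Section 6.3 (Early withdrawal of subjects), on the same patients: "any and all information gathered prior to the withdrawal will be excluded in the analysis, no further data collection will occur".
- Section 6.3 again, on patients who stop attending and cannot be reached: "then the patient is deemed lost to follow-up and any collected study data will be retained".

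Other sections say why patients may leave and how many. Section 5.6.2 lists as a secondary outcome "Patient withdrawal rates due to change in management (e.g. need for surgery", closing the bracket after that example. Section 6.1 states: "Since some patients may require surgical intervention or may withdraw, a hypothetical 20% dropout rate is calculated into the sample size". Later in the same section a different figure appears: "The calculation does take into account a 10% patient attrition rate (withdrawal and loss to follow-up", again inside a bracket.

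On the two arms, section 6.1.1 says "it is not possible to achieve blinding for the participants nor the researchers". Section 6.3 has one withdrawal rule that applies to a single arm; for a participant who becomes pregnant: "The participant will be withdrawn from the study if allocated to the Granulox arm".

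The primary comparison (sections 6.1 and 8.2) is the percentage decrease in ulcer size from baseline to week 12, by Mann-Whitney test. Weeks 3, 6 and 9 are also analysed, and section 8.3 adds a Cox regression for healing.

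**The concern.** Sections 5.3 and 6.3 cannot both be followed. An analysis plan could choose between them, but the protocol would still state both. Until it is amended, the choice could be made after outcomes are known, in a trial where nobody is blinded.

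If 6.3 is followed, a randomised patient leaves the analysis because of a later event. Sections 5.6.2 and 6.1 tie that event, at least in part, to surgery or a change in management, so it may be related to how the ulcer is doing. In an open-label trial the number of withdrawals and the reasons for them can differ by arm. The groups compared would then no longer be the groups randomised.

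The 6.3 wording covers all information, so read literally it takes withdrawn patients' adverse events and wound infections out of the safety analysis. Both are listed outcomes in section 5.6.2. The difference in treatment between a patient who announces that they are leaving and one who simply stops attending is not explained.

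**Working it through.** **1. What each rule changes.** Take a randomised patient who withdraws between the week 6 and week 9 visits.

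| Data | Under 5.3 | Under 6.3 |
|---|---|---|
| Baseline, week 3 and week 6 ulcer size | analysed | excluded |
| Contribution to the Cox model | follow-up to withdrawal available | none |
| Adverse events and infections so far | analysed | excluded |
| Week-12 ulcer size | not collected | not collected |

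The last row matters. For a patient who leaves before week 12, neither rule provides a week-12 value. Only a patient who withdraws after the week-12 visit but before the week-18 call has a week-12 value that 6.3 removes and 5.3 keeps.

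**2. How many patients.** The planned size for diabetic foot ulcers is 40. From Table 4, d = (52 − 25)/30 = 0.90. One-sided 5% and 80% power give n per arm = 2 × (1.645 + 0.842)² / 0.90² = 15.3, rounded up to 16, so 32 in total. Then 32/(1 − 0.20) = 40, as stated. (The text says two-sided, which does not give 40 after attrition. That is a separate matter.) The attrition allowance is therefore 40 − 32 = 8 patients, or 4 of 20 per arm. At the 10% figure it would be 40 × 0.10 = 4, or 2 per arm.

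**3. Size of the effect when withdrawers are left out at week 12.** The protocol gives no link between withdrawal and healing, so this is assumed and varied. Each scenario has 20,000 simulated trials: percentage decrease normal with SD 30, 20 per arm, withdrawers dropped, two-sided Mann-Whitney at 5%. *Worst* means that the poorest healers leave; *r = 0.5* means that withdrawal is moderately correlated with healing.

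| Leaving, Granulox / control | Link | Shift, no true effect (points) | Type I error | Estimate if truth is 27 | Rejection rate |
|---|---|---|---|---|---|
| 0 / 0 | none | 0 | 0.052 | 27.0 | 0.769 |
| 4 / 4 | r = 0.5 | 0 | 0.054 | 27.0 | 0.698 |
| 4 / 2 | r = 0.5 | +2.3 | 0.059 | 29.4 | 0.785 |
| 4 / 0 | r = 0.5 | +5.0 | 0.075 | 32.0 | 0.855 |
| 0 / 4 | r = 0.5 | −5.0 | 0.073 | 22.1 | 0.555 |
| 4 / 4 | worst | 0 | 0.097 | 27.0 | 0.823 |
| 4 / 2 | worst | +4.5 | 0.110 | 31.5 | 0.910 |
| 2 / 4 | worst | −4.5 | 0.112 | 22.5 | 0.680 |
| 4 / 0 | worst | +10.0 | 0.174 | 36.9 | 0.955 |
| 0 / 4 | worst | −10.0 | 0.176 | 17.0 | 0.444 |

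Hand check of the extreme rows: the mean of the upper 80% of a normal distribution lies 0.28/0.80 = 0.35 SD above the overall mean, and 0.35 × 30 = 10.5 points. The simulation with 20 per arm gives 10.0, which is 10/27 = 37% of the planned effect. In the row with the 4 worst lost from each arm the mean does not shift, yet type I error is near 10%, because the test treats the 16 left as a random sample, which they are not.

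**4. Worst-rank scoring.** If the 4 worst leave the Granulox arm and 4 at random leave the control arm, dropping them gives a shift of about 10 points and a type I error of about 0.165. Giving those 4 Granulox patients the worst rank instead brings it to about 0.032.

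**The case against.** The contradiction itself is not open to dispute. The case on the other side is against building too much on it, and most of that case stands.

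A reader might infer that 6.3 by itself raises the type I error of the primary test to about 16%, and that adopting 5.3 removes the problem. The documents do not support this. Patients who leave before week 12 lack the week-12 value under both rules, so 5.3 with available values drops the same patients. The figures in the table are the cost of missing week-12 data. The fall to about 3% comes only from worst-rank scoring, which neither section contains. How missing values are handled is commonly left to the analysis plan, and its absence from the protocol is no fault.

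A reader might also infer that 6.3 removes the worst healers. The protocol links withdrawal to surgery or change in management, which makes this plausible, but patients may leave for any reason and need not give one. No section supports a pattern in which one arm loses its worst healers and the other loses patients at random. The number affected may also be below 4 per arm: section 6.1 gives 10% as well as 20%, and patients lost to follow-up, whom the 10% figure includes, keep their data under 6.3.

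Finally, 6.3 excludes data from the analysis; it does not destroy records. Section 7.3 has every adverse event reported to the sponsor within one working day and the forms filed. The safety concern is omission from the analysis.

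None of this touches the contradiction, the unequal treatment of two kinds of dropout, or the exclusion after randomisation.

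**Conclusion.** The point holds in this form. Sections 5.3 and 6.3 conflict directly, and 6.3 as written is a post-randomisation exclusion that may be related to outcome, in an open-label trial. Its direct consequences are possible bias in the week 3, 6 and 9 comparisons and the Cox analysis, and the omission of withdrawn patients' adverse events and infections from the safety analysis. These were not quantified.

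For week 12, analysing without the withdrawers shifts the difference by 0 to about 10 points in either direction, with a two-sided type I error of about 5% to 18%. That range rests on assumptions: normal data with SD 30, 20 per arm, up to 4 withdrawals per arm, and a link to healing between moderate and complete. The direction depends on which arm loses more of its poor healers. The range shows what is at stake when withdrawers are absent at week 12; it is not the difference between the two rules.

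**What to change.** Replace the withdrawal sentence in section 6.3 with the rule of section 5.3: data collected up to withdrawal are retained and analysed, with all randomised patients in their allocated arm. State that adverse events and wound infections of every randomised patient are reported in the safety tables. This also removes the difference from patients lost to follow-up. It costs a short amendment, with no extra patients or visits, and a check that the participant information says the same.

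Optionally, add a sensitivity analysis of the week-12 Mann-Whitney comparison that gives the worst rank to patients known to have left because of surgery, amputation or ulcer deterioration. This is a choice of analysis that goes beyond aligning 6.3 with 5.3, and other approaches are defensible. Its downside is that the reason may be unknown, since patients may withhold it.

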5.4 Recruitment

Participants will be randomised to either the control group (TaU) or the intervention group (TaU plus administration of Granulox spray) for 12 weeks or until ulcer healing has been achieved. All participants will have demographic data obtained and the following base line measures (table 2):

- Foot ulcer size measured with Convatec grid tool or equivalent measuring tool
- PUSH score (size and characteristics)
- Texas University grading scores.
- Mobility score (LifeSpace questionnaire)
- Quality of life assessment using
 - o EQ-5D-5L
 - o Cardiff Wound Impact Questionnaire
 - VAS pain scale

Table 3. Overview of measurements

Weeks	-2	0	3	6*	9*	12#	18#
· Ulcar size (Converted grid))	X	Х	X	X	X	X	110-11
PUSH score	Χ	Χ	Χ	Χ	X	Χ	A48.400401-144.1
Tiexas Universading score	X	1X	X	: X	\mathbf{X}_{i}	X	
Wound healed status		Χ	Χ	Х	X	Χ	Χ
Lifte Space Questilonnaire		X		X -		X 14 3	
QoL EQ-5D-5L		Χ		Χ	The state of the s	Χ	
QoL CWIQ ************************************	Angel bir sho	1 X 1	orași d	14X1		· XD a	
VAS pain scale	X	Χ	Χ	Χ	Χ	Χ	
Patient experience questionnaire	richt sach Richer Ha d	26021	dylast.	Brutta.		X [®]	

^{*} Allowed to be up to 1 week early or late

[#] Allowed to be up to 2 weeks early or late

@Granulox arm participants only

The Pressure Ulcer Scale for Healing (PUSH) tool, see Appendix 1 is a standardised method of assessing and monitoring the severity and healing of both pressure ulcers and venous leg ulcers (Stotts et al, 2001; Ratliff & Rodeheaver 2005). The Pressure Ulcer Scale for Healing (PUSH) is a valid, responsive, evaluative tool to monitor and document wound progress of foot ulcers (Hon, 2010). Findings also suggest that total PUSH scores predict time-to-heal for foot ulcers (Gardner 2011).

A mobility measure will be taken using a life space questionnaire, see Appendix 1 (Stalvey *et al* 1999). This is a tool that has demonstrated reliability and construct and criterion validity in establishing the spatial extent of an older person's mobility within their home setting. There are other versions (Peel *et al* 2005) that additionally measure the use of aids and equipment however this is not of particular interest within the study, hence the simpler version will be used.

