A recent review of specific health related quality of life instruments for venous leg ulcers favours the Charing Cross Venous Leg Ulcer Questionnaire (Appendix 2) (Smith *et al* 2010) above others such as the Hyland for its disease specific psychometric characteristics (Gonzalez & Verdu 2011).

5.5 **Follow-up**

Patients are in the study for a period of 18 weeks. Thereafter, the patient will be followed up as they would be in normal clinical practice. During and after the trial, clinical staff will redress the wound as per routine care, and during the trial they will conduct the measurement of the foot ulcer (grid measurement tool, Texas Univ grading and PUSH score). The researcher will be in attendance at -2 weeks, 0 weeks, and weeks 3,6,9,12 of study participation to randomise the patient, issue the Granulox spray if indicated, and conduct/collect the study participant questionnaires. The researcher will phone the participant at week 18 to check on wound status and any adverse event reporting.

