5.6 Outcome measures

5.6.1 Primary outcome measures

The primary outcome for this trial will be the efficacy of the Granulox spray in terms of wound healing.

Foot ulcer size, measured with Convated grid tool (week -2, 0, 3, 6, 9, 12)

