7.3 Procedures for recording adverse events

All AEs need to be reported to the sponsor/host Trust R&D within one working day of the investigator team becoming aware of them. For this purpose an AE report form is completed by the researcher and/or Chief Investigator

The relationship of each adverse event to the trial must be determined by the Chief Investigator, a medically qualified individual, according to the following definitions:

- Related: The adverse event follows a reasonable temporal sequence from swabbing. It cannot reasonably be attributed to any other cause.
- **Not Related**: The adverse event is probably produced by the participant's clinical state or by other modes of therapy administered to the participant.
- Severity grading: the Chief Investigator will also record if it concerns an AE or SAE.

This is recorded on the aforementioned AE reporting form. The forms are stored in the study site file.

Pseudo-anonymised copies of all adverse events forms will be shared with InFirst as soon as causality reporting has been performed and concluded.

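### Section 6.3 withdraws a pregnant Granulox participant from the study instead of only from the device, so device-free scheduled follow-up is lost in one arm

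*Protocol*

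**What the plan says.** - **Pregnancy during the trial (6.3).** A participant who finds she is pregnant is asked to tell the research team at once. Then: "The participant will be withdrawn from the study if allocated to the Granulox arm". No matching rule is given for the control arm.
- **Pregnancy at entry (6.2.2).** The exclusions include "Patient pregnant, actively planning to become pregnant, or lactating".
- **Treatment period (5.4).** Participants receive their allocated treatment "for 12 weeks or until ulcer healing has been achieved".
- **Study period (5.5).** "Patients are in the study for a period of 18 weeks". At the end, "The researcher will phone the participant at week 18 to check on wound status and any adverse event reporting".
- **Primary outcome (5.6.1, 6.1, 8.2).** Ulcer size by measuring grid, with week 12 as the primary endpoint.
- **Self-withdrawal (6.3).** For a patient who withdraws from the trial, "no further data collection will occur". The section does not say whether this also governs a withdrawal made by the team.
- **Adverse events (7.3).** All must be reported "within one working day of the investigator team becoming aware of them".

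**The concern.** Stopping a device and leaving a trial are different things. Pregnancy is a good reason for the first. It is not in itself a reason for the second when the remaining assessments are wound measurements, questionnaires and a phone call. Section 6.3 runs the two together, and no other section offers a route to stop Granulox and stay in follow-up.

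Two things are at stake, both modest. First, the rule removes patients after randomisation in one arm only, so any data it costs are missing because of allocation. Second, the person removed is the one who was exposed, and she loses her remaining scheduled contacts, including the only one that names adverse events.

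**Working it through.** **1. Does the remaining follow-up need the device?**

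Table 3 lists ulcer size, PUSH, Texas grade, healed status, pain score, LifeSpace, EQ-5D-5L and CWIQ. The control arm completes all of these, and the week 18 call, without Granulox. The only Granulox-specific item is the week 12 experience questionnaire, which is left out of the counts below. Section 6.3 has no rule removing a pregnant control participant, so the protocol does not treat these assessments as unsuitable in pregnancy.

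**2. Is off-device follow-up already part of the plan?**

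Yes. Treatment lasts up to 12 weeks or until healing (5.4), and participation lasts 18 weeks (5.5). A participant who completes treatment still has the week 18 call to come, and an early healer has more contacts. This shows only that such follow-up is practicable. It does not show that the authors intended it after a stop for safety.

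**3. What is lost per case?**

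Table 3 entries per contact:
- Week 3: size, PUSH, Texas, healed status, pain = 5
- Week 6: these five plus LifeSpace, EQ-5D-5L and CWIQ = 8
- Week 9: 5
- Week 12: 8
- Week 18: healed status = 1

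| Withdrawn just after | Entries lost | Contacts lost | Week 12 primary measurement |
|---|---|---|---|
| Week 0 | 5+8+5+8+1 = 27 | 5 | lost |
| Week 3 | 8+5+8+1 = 22 | 4 | lost |
| Week 6 | 5+8+1 = 14 | 3 | lost |
| Week 9 | 8+1 = 9 | 2 | lost |
| Week 12 | 1 | 1 | kept |

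Most of these entries are efficacy measures or questionnaires. Those with safety content are the Texas grade, which records infection, and the week 18 call.

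**4. How many cases?**

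The protocol gives no pregnancy rate. Given the entry exclusions, 0 to 1 is assumed.

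**5. What does one case do to power?**

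Inputs from section 6.1 and Table 4: 52% against 25%, SD 30%, so d = 27/30 = 0.90.

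The planned 40 diabetic foot ulcer (DFU) patients reproduce with the one-tailed approach named in Table 4: n per arm = 2 × (1.645 + 0.842)² / 0.90² = 15.3, rounded up to 16. Then 32/0.8 = 40.

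For the effect of one loss I use the two-sided 5% Mann-Whitney test stated in the text of 6.1. Each arm size is multiplied by 3/π = 0.955 to give a and b. Power then comes from a noncentral t with a + b − 2 degrees of freedom and noncentrality 0.90 × √(ab/(a+b)).

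| Analysed, Granulox vs control | Power | After losing one Granulox patient |
|---|---|---|
| DFU, 20 vs 20 | 77.2% | 76.1% |
| DFU, 16 vs 16 (after 20% attrition) | 67.1% | 65.6% |
| All, 30 vs 30 | 91.7% | 91.3% |
| All, 24 vs 24 (after 20% attrition) | 84.6% | 83.8% |

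The largest fall is 67.1 − 65.6 = 1.5 points. The last two rows assume that the DFU effect and SD also hold in the 20 non-DFU patients, whom section 6.1 recruits as a pilot. The two attrition rows count her on top of the 20% allowance. That allowance already covers withdrawals, so they are upper bounds.

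**The case against.** The strongest reply is that this is a preference, not an error. Section 6.3 is clear about who is withdrawn and why, contradicts no other pregnancy rule, and fits the entry exclusion. Ending participation when someone no longer meets an entry criterion is a conservative choice. That is fair as far as it goes, and it holds the severity down. It does not show that leaving the study protects her: stopping the spray already ends the exposure.

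A second reply is that the safety gain is thin. This largely stands. Only the week 18 call names adverse events, section 7.3 still requires reporting of events the team learns of, and follow-up to week 18 would end before most pregnancy outcomes are known.

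Some stronger readings are tempting, but the document does not support them:
- **That 6.3 orders all her data collection to stop and her earlier data to be discarded.** Those clauses are written for a patient who withdraws herself. Applying them to a withdrawal by the team is an inference. That her remaining visits end is the natural meaning of being withdrawn from the study, but 6.3 does not spell it out.
- **That naming only the Granulox arm is itself the fault.** It is not, because only that arm has an exposure to stop.
- **That the rule threatens the primary comparison or switches off safety reporting.** With 0 to 1 cases it does not do the first, and section 7.3 rules out the second.

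**Conclusion.** The point holds as a small, inexpensive improvement. Section 6.3 ends study participation where stopping the device would do. On its natural reading an exposed participant loses up to 27 scheduled entries at 5 contacts, including the week 12 primary measurement unless she is withdrawn after that visit. A pregnant control participant loses none.

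The effect on power and bias is negligible: at most about 1.5 points for one case, and probably less because the dropout allowance can absorb her. The benefit is limited to removing an allocation-dependent loss of data and keeping infection grading and the week 18 adverse-event call for someone who was exposed.

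This rests on two assumptions: that 0 to 1 pregnancies occur, and that withdrawal from the study means the scheduled visits stop.

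**What to change.** Reword the pregnancy paragraph in section 6.3 to say that:
- on pregnancy, Granulox is stopped permanently;
- the participant stays in the already scheduled follow-up to week 18 unless she withdraws consent;
- her data are kept and analysed in her randomised arm;
- the pregnancy is recorded as safety information.

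Collecting the pregnancy outcome after week 18 would be a useful option but is not needed for this point. It would require its own consent wording.

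**Cost.** A one-paragraph amendment, which needs prior approval from the review bodies (10.1). It adds no visits, since at most 5 already scheduled contacts per case are kept, but recording the pregnancy is one extra data item. The consent pages are not available here, so their wording on pregnancy should be checked and aligned if it describes withdrawal. With recruitment due to end on 31 January 2019, the change is best combined with any other amendment to section 6.3.
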